6.5.2. Matching method

For matching the full cohort, concomitant use of metformin at index date will be an exact matching variable.

Matching will be carried out in several rounds to achieve the highest possible matching ratio given the available data in each country (up to 1:3 matching). In the first round of matching, for each empagliflozin initiator i_E with index date T_{i_E} , all individuals initiating DPP-4 inhibitors within 3 months (90 days) before or after T_{i_E} and with the same status of concomitant metformin use at T_{i_E} will be eligible as comparators. For UK CPRD data, only individuals from the same database (GOLD or Aurum) as the empagliflozin initiator will be considered as eligible comparators. Of these, the individual with the closest propensity score(s) to that of i_E within a predefined propensity score interval will be selected (Greedy matching method). In case of ties, the selection will be made randomly. After each round of selection, the selected comparators are then removed from the pool of possible comparators for further selection (sampling without replacement) [5].

The predefined propensity score interval will be calculated based on the standard deviation of the logit of propensity score δ multiplied by a coefficient k . The value of the coefficient k will be initially set to 0.2, i.e. using a caliper of 0.2 standard deviations (i.e. 0.2 δ). The coefficient k will then be calibrated to ensure at least 99% of empagliflozin initiators have matches from initiators of DPP-4 inhibitors after the first round of propensity score matching [6]. The same calibrated matching caliper $k\delta$ used in the first matching round will be reused in the second and third matching rounds.

Matching by time-period, based on index dates, enables better control of time-varying confounders including changing prescription patterns for empagliflozin and potential confounding. In case there is a strong time bias in the number of matches per empagliflozin user (e.g., initiators in early years have more matches than initiators from later years), a relaxation of the criteria for matching within time-period will be considered. In addition, the criteria for calibrating coefficient k may be modified if the data does not allow matching of 99% of empagliflozin initiators.

6.6. ASSESSING THE QUALITY OF THE MATCHING

6.6.1. Propensity score distribution before and after matching and common support region

For each propensity score set (all patient cohort and concomitant metformin users cohort), the propensity score distribution will be plotted for empagliflozin users and DPP-4 inhibitor users before matching (Figure 3). This will be used for visual inspection of the common support region.

The propensity score distribution in non-matched empagliflozin users, matched empagliflozin users, and matched DPP-4 inhibitor users will be plotted for each cohort in each country. Results will be presented in 2 plots similar to Figure 5, one for each of the two propensity score matched cohorts.

6.6.2. Assessment of covariate balance before and after matching

The covariates balance between treatment groups before and after matching will be evaluated using:

- Standardized differences (percentage).
- χ^2 test for equality of proportions in dichotomous variables (p-value).
- t-test for equality of means in continuous variables (p-value).

For continuous variables, the standardized difference is defined as

$$d = \frac{(\bar{x}_{\text{empagliflozin}} - \bar{x}_{\text{DPP-4 inhibitor}})}{\sqrt{\frac{s_{\text{empagliflozin}}^2 + s_{\text{DPP-4 inhibitor}}^2}{2}}} \times 100$$

Where $\bar{x}_{\text{empagliflozin}}$ and $\bar{x}_{\text{DPP-4 inhibitor}}$ denote the sample mean of the covariate in empagliflozin users at index date and comparison drug users at index date, respectively, while $s_{\text{empagliflozin}}^2$ and $s_{\text{DPP-4 inhibitor}}^2$ denote the sample variance of the covariate in empagliflozin users at index date and comparison drug users at index date, respectively.

For dichotomous variables, the standardized difference is defined as

$$d = \frac{(\hat{p}_{\text{empagliflozin}} - \hat{p}_{\text{DPP-4 inhibitor}})}{\sqrt{\frac{\hat{p}_{\text{empagliflozin}}(1 - \hat{p}_{\text{empagliflozin}}) + \hat{p}_{\text{DPP-4 inhibitor}}(1 - \hat{p}_{\text{DPP-4 inhibitor}})}{2}}} \times 100$$

Proprietary confidential information © 2024 Boehringer Ingelheim International GmbH or one or more of its affiliated companies

Where $\hat{p}_{empagliflozin}$ and $\hat{p}_{DPP-4\ inhibitor}$ denote the prevalence of the dichotomous variable in empagliflozin users at index date and DPP-4 inhibitor users at index date, respectively [7]

If a categorical variable is defined with more than two categories (i.e. not dichotomous), each category will be treated as a dichotomous variable when computing the standardized differences.

The balance assessment will be performed with regard to the following covariates:

- Demographics and other baseline characteristics at index date Table 11.
- Diabetic complications Table 12 (status at index date).
- Non-diabetic concomitant disease Table 13 (status at index date).
- Diabetic concomitant medication use Table 14 (status at index date).
- Non-diabetic concomitant medication use Table 15 (status at index date).

Balance in baseline characteristics before and after matching between empagliflozin users at index and the DPP-4 inhibitor users at index will be reported in each country, separately.

All continuous variables will be described using standard statistical measures, i.e. range, mean, standard deviation, median, first and third quartile. All categorical variables will be summarized with absolute and relative frequencies. The standardized differences and p-values for the statistical tests will be also reported.

Results will be reported in 4 tables similar to Table 18.

Standardized difference < 10% will be used as indicator of satisfactory distribution balance after matching [8]. Variables with standardized difference larger than 10% might still exist. The unbalanced variables will be considered as potential confounders and included in the adjustment of Cox's PH model, as described in the comparative analysis (Section 6.7.2). In case a substantial amount of variables remain unbalanced, the PS matching procedure will be re-evaluated by, for example, reducing the caliper width.

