6.7.2. Comparative analysis

Hazard ratios (HRs) for the outcomes defined in Table 8 will be estimated for PS matched cohorts using Cox's PH model with time-varying covariates, if model pre-requisites are fulfilled. HRs will be presented along with 95% CIs. Proportional hazards assumptions for time-fixed exposure variables will be assessed for each model by plotting scaled Schoenfeld residuals.

The comparative analyses will be performed separately for the matched full cohort and matched metformin-user cohort.

Crude model

Crude HRs are calculated using a Cox PH model with as-treated exposure (as defined in Section 5.1.7) as the only included variable.

HRs estimated using the crude model will be presented along with 95% CIs. A table template for the result is given in Table 23. Analysis will be performed separately for each country.

Crude HRs with 95% CIs will be collected from all study countries to carry out meta-analyses as described in Section 6.7.3.2. Results will be reported as in Figure 8.

Base model

Based on the crude model, the base model will be further adjusted with the unbalanced covariates at index date (standard difference $\geq 10\%$) among the variables included in the propensity score model (Section 6.6). The inclusion of adjusting variables will be considered based on data availability as described in Section 10.

HRs estimated using the base model will be presented along with 95% CIs. A table template for the result is given in Table 24. Analysis will be performed separately for each country. HRs with 95% CIs estimated using base model will be collected from all study countries to carry out meta-analyses as described in Section 6.7.3.2. Results will be reported as in Figure 8.

Adjusted model

The base model will be further adjusted with selected time-dependent variables. The following time-dependent variables will be initially considered for inclusion (as detailed in Section 9) in the adjusted Cox's PH model:

- HbA1c value (as defined in Table 11)
- Kidney or genitourinary stones (as defined in Table 13)
- UTI or pyelonephritis (as defined in Table 13)
- Ever exposed to insulin (as defined in Table 14)
- Ever exposed to metformin (as defined in Table 14)

Proprietary confidential information © 2024 Boehringer Ingelheim International GmbH or one or more of its affiliated companies

- Ever exposed to other glucose lowering medication (as defined in Table 14)
- Ever exposed to GLP-1 drugs (as defined in Table 14)

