- Ever exposed to thiazolidinediones (as defined in Table 14)
- Ever exposed to sulfonylureas (as defined in Table 14)

HRs estimated using the adjusted model with time-dependent covariates will be presented along with 95% CIs. A table template for the result is given in Table 25. Analysis will be performed and model adjustment will be applied separately for each country.

Adjusted HRs with 95% CIs will be collected from all study countries to carry out meta-analyses as described in Section 6.7.3.2. Results will be reported as in Figure 8.

Handling of model convergence failure

For outcomes with a small number of events, convergence failure of multivariable Cox PH regression model may happen if there are no events for a particular combination of covariate values. Thus, a minimum of 5 outcome events per category of a variable is required for it to be included in the Cox model. In case of persisting model convergence failure while meeting this minimum requirement, the included covariates will be removed sequentially based on the rank of their PS standardised differences. The covariate with the smallest standardised difference will be removed iteratively until the model converges. In case of ties in selection, the choice is made randomly. The removed covariates will be reported along with the HR estimates.

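### The standardized difference carries a sign, but the balance, adjustment and removal rules use it without absolute value, so negative imbalances can pass as balance

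*SAP*

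**What the plan says.** SAP 6.6.2 gives two explicit formulas, introduced by "For continuous variables, the standardized difference is defined as" and "For dichotomous variables, the standardized difference is defined as". In both, the numerator is the empagliflozin value minus the DPP-4 inhibitor value, the denominator is the square root of the average of the two variances, and the ratio is multiplied by 100. Neither has absolute-value bars. For a variable with more than two levels, "each category will be treated as a dichotomous variable when computing the standardized differences".

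These decisions then rest on d:

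- **Balance (6.6.2).** "Standardized difference < 10% will be used as indicator of satisfactory distribution balance after matching". Imbalance is restated as "Variables with standardized difference larger than 10% might still exist". If many variables stay unbalanced, the matching is to be re-evaluated.
- **Entry to the base model (6.7.2).** "the base model will be further adjusted with the unbalanced covariates at index date", with a threshold of 10% or more.
- **Removal on persistent convergence failure (6.7.2).** Included covariates are ranked by standardized difference. "The covariate with the smallest standardised difference will be removed iteratively until the model converges".

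No readable part of either document says that the absolute value is meant. The footnote on model adjustment in Protocol Table 4 speaks only of covariates that are not balanced after matching and gives no direction.

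**The concern.** A signed quantity compared with a one-sided threshold detects imbalance in one direction only. Any d below zero is also below 10%, however large the difference.

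The 10% test is the gate for baseline covariates into the base model, and the adjusted model is built on that set. SAP Section 3 (change no. 8) explains that restricting adjustment to unbalanced confounders is deliberate, because few events are expected for outcomes such as renal cancer. A baseline confounder that wrongly passes the test is therefore not picked up by a broader adjustment set, unless it is also on the fixed list of time-dependent covariates. The same covariate also fails to count towards the trigger for re-evaluating the matching. The chi-square and t-test p-values are reported, but none of these decisions uses them.

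**Working it through.** There is no figure in the plan to reproduce. The check applies the SAP formulas to example values, first with the sign as written and then with |d|. **All covariate values in steps 1 to 4 are assumptions**, because the documents give no covariate distributions.

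**1. Yes/no covariate, 20% versus 30%.**
d = 100 × (0.20 − 0.30) / √[(0.20×0.80 + 0.30×0.70)/2] = −10 / √0.185 = −23.2%.
Mirror case, 30% versus 20%: d = +23.2%.

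| Case | d | As written | With \|d\| |
|---|---|---|---|
| 20% vs 30% | −23.2% | balanced, not adjusted | unbalanced, adjusted |
| 30% vs 20% | +23.2% | unbalanced, adjusted | unbalanced, adjusted |

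The template in SAP Table 18 shows one standardized difference for each yes/no variable. For comorbidities, SAP Section 9 reads a missing code as absence of the condition, so these variables stay dichotomous and have a single d.

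**2. Continuous covariate that is also banded.** Take age as normal with SD 11, using the SAP Table 11 bands.

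- Mean 60 versus 65: d = 100 × (−5)/11 = −45.5%, which passes as balanced. The bands give +28.2% (18-49) and +16.1% (50-64), so banded age is still flagged.
- Mean 61.5 versus 63: d = 100 × (−1.5)/11 = −13.6%, which passes as balanced. The bands from youngest to oldest give +8.6, +4.7, −2.8, −4.5, −5.1, −4.6 and −4.6%. None reaches +10%, so this imbalance is missed both ways.

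**3. Base-model entry.** Take five single-d covariates: A −25, B −12, C +2, D +11, E +18. As written, the base model takes D and E. With |d| it takes A, B, D and E.

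**4. Removal order.** Suppose all five are in a model that fails to converge.

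- Signed order: A, B, C, D, E. The worst-balanced covariate goes first.
- |d| order: C, D, B, E, A. The worst-balanced covariate goes last.

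Under the literal entry rule, A and B could be in the model only by another route. They could be on the fixed time-dependent list in 6.7.2 (HbA1c, stones, UTI, ever use of insulin and others), ranked here by their index-date d. Or they could be multi-category variables that entered through a different category.

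**The case against.** The strongest reply is that magnitude was plainly meant. The SAP speaks of unbalanced variables and of satisfactory balance, neither of which has a direction. For sex or any yes/no item the sign depends only on which level is coded, so a signed rule would make no sense. Every d is tabulated and a second statistician checks the programs, so a large negative value would be visible. The plot template in SAP Figure 4 is not shown, so whether it displays absolute values cannot be checked. This reply makes literal coding less likely, but it does not override an explicit signed formula. SAP Section 10 has the checking statistician confirm that the analysis follows the SEAP. A literal program would pass that check, and one using |d| would depart from the stated definition.

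The objection does succeed against several stronger readings that a reader might infer:

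- **That every covariate lower with empagliflozin is missed.** A deficit in one category means an excess in another, which can exceed +10%. Renal impairment derives from eGFR, so less impairment would tend to show as positive d on eGFR. A partly missing yes/no variable gains a missing category under SAP Section 9.
- **That a covariate is both passed as balanced and dropped first.** A single-d covariate with negative d never enters through the 10% rule, so there is nothing to drop. Early removal reaches only the two groups in step 4. It needs convergence failure that persists after the requirement of 5 events per category, and removals are reported.
- **That these rules alone choose the confounders.** The time-dependent list, the 5-event minimum and the missing-data rule also matter, and propensity score matching is the main control.
- **That half of all imbalances are missed.** This would need imbalances to be equally likely in both directions and would ignore multi-category variables. The documents support neither.
- **That Protocol Table 6 shows the impact.** For index year 2015 its counts give d = −48.3% in Sweden (629/32,334 versus 10,305/68,481) and −81.5% in Finland (91/18,269 versus 14,130/54,079). These are values before matching. SAP 6.3 makes index year an exact matching criterion, and 6.5.2 restricts comparators to 90 days either side. Even on the signed rule, later years would flag the variable: 2018 to 2020 give about +20, +34 and +34% in Sweden.

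**Conclusion.** The point stands in limited form. Followed as written, SAP 6.6.2 and 6.7.2 treat a dichotomous covariate as balanced when it is lower in empagliflozin users by 10% or more after matching. The same applies to a continuous covariate that its bands or a related variable do not flag. Such a covariate is left out of the base model and does not count towards re-evaluating the matching. On persistent convergence failure, listed time-dependent covariates, or multi-category ones that entered through another category, would be removed ahead of better-balanced ones if their d is strongly negative.

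This is a stated rule that gives the wrong answer and conflicts with the plan's own aim. It is not evidence that the analysis will be, or was, run on signed values. The size of any bias cannot be derived from the documents: it depends on literal coding and on how many covariates keep a negative imbalance after matching. If matching leaves no such covariate at or beyond −10%, the balance and entry rules give the same result either way, although the removal order could still differ.

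**What to change.** Change the SAP text as follows.

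- **6.6.2:** define satisfactory balance as |d| < 10%, and restate imbalance in terms of |d|, so that the trigger to re-evaluate the matching also uses it.
- **6.7.2, base model:** adjust for covariates with |d| of 10% or more.
- **6.7.2, convergence failure:** remove the covariate with the smallest |d| first. Rank a multi-category variable by the largest |d| over its categories.

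The cost is a few words in the SAP and a check that the programs take the absolute value. No extra data or analyses are needed.

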6.7. AS-TREATED ANALYSIS

6.7.1. Descriptive analysis

Crude incidence rates (IRs) for the outcomes defined in Table 8 will be estimated within each exposure category as defined in Table 5 using Poisson regression.

In addition, stratified IRs will be derived for the following variables:

- Demographics and other baseline characteristics at index date Table 11.

Proprietary confidential information © 2024 Boehringer Ingelheim International GmbH or one or more of its affiliated companies

- Diabetic complications Table 12.
- Non-diabetic concomitant disease Table 13.
- Diabetic concomitant medication use Table 14.
- Non-diabetic concomitant medication use Table 15.

Crude IRs will be presented along with 95% CIs. Other descriptive summaries such as number of events and person-time for calculating the IR will be included. Analysis will be performed for each country. Results will be reported as in Table 22.

Kaplan-Meier plots, with 95% CIs, for event-free survival probabilities will be presented for each country for the outcomes defined in Table 8 with exposures as defined in Table 5. Results will be reported as the figure template shown in Figure 6.

Meta-analyses of IRs will be carried out using aggregated data across countries as described in Section 6.7.3.1 and reported as shown in Table 22.

6.7.2. Comparative analysis

Hazard ratios (HRs) for the outcomes defined in Table 8 will be estimated for PS matched cohorts using Cox's PH model with time-varying covariates, if model pre-requisites are fulfilled. HRs will be presented along with 95% CIs. Proportional hazards assumptions for time-fixed exposure variables will be assessed for each model by plotting scaled Schoenfeld residuals.

The comparative analyses will be performed separately for the matched full cohort and matched metformin-user cohort.

Crude model

Crude HRs are calculated using a Cox PH model with as-treated exposure (as defined in Section 5.1.7) as the only included variable.

HRs estimated using the crude model will be presented along with 95% CIs. A table template for the result is given in Table 23. Analysis will be performed separately for each country.

Crude HRs with 95% CIs will be collected from all study countries to carry out meta-analyses as described in Section 6.7.3.2. Results will be reported as in Figure 8.

Base model

Based on the crude model, the base model will be further adjusted with the unbalanced covariates at index date (standard difference $\geq 10\%$) among the variables included in the propensity score model (Section 6.6). The inclusion of adjusting variables will be considered based on data availability as described in Section 10.

HRs estimated using the base model will be presented along with 95% CIs. A table template for the result is given in Table 24. Analysis will be performed separately for each country. HRs with 95% CIs estimated using base model will be collected from all study countries to carry out meta-analyses as described in Section 6.7.3.2. Results will be reported as in Figure 8.

Adjusted model

The base model will be further adjusted with selected time-dependent variables. The following time-dependent variables will be initially considered for inclusion (as detailed in Section 9) in the adjusted Cox's PH model:

- HbA1c value (as defined in Table 11)
- Kidney or genitourinary stones (as defined in Table 13)
- UTI or pyelonephritis (as defined in Table 13)
- Ever exposed to insulin (as defined in Table 14)
- Ever exposed to metformin (as defined in Table 14)

Proprietary confidential information © 2024 Boehringer Ingelheim International GmbH or one or more of its affiliated companies

- Ever exposed to other glucose lowering medication (as defined in Table 14)
- Ever exposed to GLP-1 drugs (as defined in Table 14)
- Ever exposed to thiazolidinediones (as defined in Table 14)
- Ever exposed to sulfonylureas (as defined in Table 14)

HRs estimated using the adjusted model with time-dependent covariates will be presented along with 95% CIs. A table template for the result is given in Table 25. Analysis will be performed and model adjustment will be applied separately for each country.

Adjusted HRs with 95% CIs will be collected from all study countries to carry out meta-analyses as described in Section 6.7.3.2. Results will be reported as in Figure 8.

Handling of model convergence failure

For outcomes with a small number of events, convergence failure of multivariable Cox PH regression model may happen if there are no events for a particular combination of covariate values. Thus, a minimum of 5 outcome events per category of a variable is required for it to be included in the Cox model. In case of persisting model convergence failure while meeting this minimum requirement, the included covariates will be removed sequentially based on the rank of their PS standardised differences. The covariate with the smallest standardised difference will be removed iteratively until the model converges. In case of ties in selection, the choice is made randomly. The removed covariates will be reported along with the HR estimates.

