1. INTRODUCTION

This statistical analysis plan refers to the final version of the pharmacoepidemiological study protocol entitled “Post-authorisation safety study to assess the risk of urinary tract malignancies in relation to empagliflozin exposure in patients with type 2 diabetes: a multi-database European study”, version 6.0 dated February 10th, 2022 unless otherwise stated.

This is an observational, comparative cohort safety study based on European healthcare databases and includes databases from the UK, Sweden and Finland.

The study will use a new user design to compare new users of empagliflozin to new users of DPP-4 inhibitors in order to assess the risk of urinary tract malignancies.

Individuals with similar treatment and clinical history will be matched by deriving propensity scores conditional on factors potentially affecting the treatment and outcome.

In the primary analysis, propensity-score (PS) matched cohorts will be derived from the study base by matching patients who initiate empagliflozin with patients who initiate DPP-4 inhibitors at index date with a variable matching ratio of up to 1:3 (1:1 matching in a sensitivity analysis) using greedy matching methods.

In addition, patients using metformin in free or fixed dose combination with empagliflozin or with a DPP-4 inhibitor will be identified and the primary analysis will be repeated within this subset of patients.

Proprietary confidential information © 2024 Boehringer Ingelheim International GmbH or one or more of its affiliated companies

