2.2. OBJECTIVES

Primary objectives

- i. To estimate the adjusted hazard ratio and incidence rates of all urinary tract cancers (bladder, renal and other urinary tract cancers) in patients initiating empagliflozin compared to patients initiating a DPP-4 inhibitor.
- ii. To estimate the adjusted hazard ratios and incidence rates of bladder cancer in patients initiating empagliflozin compared to patients initiating a DPP-4 inhibitor.
- iii. To estimate the adjusted hazard ratios and incidence rates of renal cancer in patients initiating empagliflozin compared to patients initiating a DPP-4 inhibitor.

Secondary objectives

- i. To estimate the adjusted hazard ratio and incidence rates of each primary outcome (all urinary tract cancers, bladder cancer, renal cancer) with respect to:
 - a. Increasing cumulative dosage to empagliflozin.
 - b. Dosage of empagliflozin prescribed per use (10mg vs. 25mg).
 - c. Time since first prescribed/dispensed dose of empagliflozin.

Proprietary confidential information © 2024 Boehringer Ingelheim International GmbH or one or more of its affiliated companies

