6.3. METHODS ADDRESSING BIAS

Potential biases will be addressed as follows:

- Selection bias and immortal time bias is addressed thru the study design. It include a new user cohort design, a selection of comparator drugs with the same indication and prescribed to patients with potentially similar T2D disease severity, and a definition of exposure and study entry based on information before or at index date.
- Channeling bias is addressed by using propensity score matching to construct balanced exposure groups. In addition, the year of the index date (date of first prescription of the study group) is used as an exact matching criteria.
- Bias due to definitions of exposure, definition of follow-up times and other relevant covariates will be addressed through sensitivity analyses.

Proprietary confidential information © 2024 Boehringer Ingelheim International GmbH or one or more of its affiliated companies

- Diagnostic bias will be evaluated and addressed in sensitivity analyses through consideration of the frequency of urine dipstick testing (as captured through albuminuria tests) and stage of cancer at the time of diagnosis (as more early-stage cancers in one group would be suggestive of diagnostic bias).

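### Crude hazard ratios, incidence rates and Kaplan-Meier curves compare raw pools after 1-to-3 matching, and the pooled incidence rates give the two drugs different country mixes

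*SAP*

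**What the plan says.** SAP section 1 sets the primary design as propensity-score matching "with a variable matching ratio of up to 1:3 (1:1 matching in a sensitivity analysis) using greedy matching methods". Under SAP 6.5.2 the candidates for each empagliflozin initiator are "all individuals initiating DPP-4 inhibitors within 3 months (90 days) before or after" the index date, taken over up to three rounds without replacement. SAP 6.3 instead says that "the year of the index date (date of first prescription of the study group) is used as an exact matching criteria".

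SAP 6.5.2 foresees that early initiators may collect more matches than late ones. Its response is that "a relaxation of the criteria for matching within time-period will be considered".

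For the analysis, SAP 6.7.2 states: "Crude HRs are calculated using a Cox PH model with as-treated exposure (as defined in Section 5.1.7) as the only included variable". SAP 6.7.1 takes crude incidence rates and Kaplan-Meier curves by exposure group. SAP 6.6.2 computes standardized differences from plain sample means and prevalences; for multi-level variables, "each category will be treated as a dichotomous variable when computing the standardized differences". Its limit is 10%, and "The unbalanced variables will be considered as potential confounders and included in the adjustment of Cox's PH model". SAP 6.7.3.1 defines the pooled incidence rate as total events over total person-time across countries, and the Table 22 shell reports it by drug.

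Rates are part of each primary objective. The first reads: "To estimate the adjusted hazard ratio and incidence rates of all urinary tract cancers". Crude hazard ratios are also meta-analysed (SAP 6.7.2).

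**The concern.** When set size varies, the two groups are comparable within sets, or after each comparator is weighted by 1/(number of comparators in its set). They are not comparable as raw pools. Patients whose empagliflozin match found three comparators count three times in the DPP-4 pool and once in the empagliflozin pool. Set size falls with calendar time, because empagliflozin initiation rises while DPP-4 initiation falls. The raw DPP-4 pool is therefore tilted towards early index years. Exact year matching does not prevent this: it equalises year inside each set, not across pools.

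The pooled rates carry a second imbalance. The achieved matching ratio differs by country, so summed DPP-4 person-time has a different country mix from summed empagliflozin person-time, and the protocol's own rates differ by country.

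At stake are outputs that receive no covariate adjustment: crude hazard ratios, by-drug rates and survival curves in a safety report. A reader could see a pooled rate excess that the pooled hazard ratio does not show.

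**Working it through.** **Plan's own figure.** Protocol Table 7 power can be reproduced with a Wald test on the log hazard ratio: variance = 1/E0 + 1/E1, two-sided 5%, time at risk = stated follow-up less the 6-month lag. For Sweden, urinary tract cancer, HR 1.5: E0 = 32,334 × 1.7 × 164.5/100,000 = 90.4 and E1 = 1.5 × 90.4 = 135.6. The standard error is 0.136 and power is 84.8% (Table 7: 85.1%). Finland at 1:2 gives 80.3% (Table 7: 80.6%). The cost estimates under the fix use this formula.

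**Index-year mix.** Inputs are the yearly eligible counts e (empagliflozin) and d (DPP-4) in protocol Table 6. Assume same-year matching and ignore the caliper, the metformin match and the lag exclusions. Matched empagliflozin = min(e, d); matched DPP-4 = min(3e, d). The standardized difference follows SAP 6.6.2.

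Sweden, 2017: p = 4,811/31,216 = 15.4%; q = 13,677/51,266 = 26.7%. The difference of -11.3 points divided by √[(0.1304 + 0.1956)/2] = 0.404 gives -27.9%.

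| Source | Mean set size, 2016 to 2020 | Lowest | Highest |
|---|---|---|---|
| Sweden | 3.0, 2.8, 1.5, 1.1, 1.0 | -28% (2017) | +22% (2019) |
| Finland | 3.0, 2.0, 1.6, 1.2, 1.0 | -26% (2016) | +20% (2019) |
| CPRD GOLD | 3.0, 3.0, 2.7, 2.0, 1.4 | -15% (2017) | +21% (2021) |

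Yearly counts for CPRD Aurum are not given. With 1/(set size) weights the same-year differences are zero.

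A simulation of the 90-day window, with initiation spread evenly within years and the propensity score ignored, gives similar extremes: Sweden -28%/+23%, Finland -31%/+23%, GOLD -14%/+21%. After weighting, the largest absolute values are about 6%, just under 10%, and 5%.

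**Effect on crude rates.** This needs an assumption that is not in the documents: the event rate changes by a factor (1 + g) per index year. Person-time runs from 6 months after index to data end. With no drug effect, the crude rate ratio is:
- g = ±2%: within 0.992-1.008 in every source.
- g = ±5%: 0.98-1.02 (Sweden, Finland) and 0.99-1.01 (GOLD).
- g = ±10%: 0.96-1.04 (Sweden), 0.97-1.03 (Finland) and 0.98-1.03 (GOLD).

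**Pooled rates.** Inputs, in the order UK, Sweden, Finland: initiators 16,887, 32,334, 18,269 (protocol abstract); time at risk 1.9, 1.7, 1.9 years; protocol rates per 100,000 person-years of 111.5, 164.5, 161.5 (urinary tract), 66.7, 104.1, 86.8 (bladder) and 26.5, 58.0, 71.6 (renal). Ratios from the 90-day simulation are 2.22 (GOLD value used for the UK), 1.63 and 1.71. If Aurum reached 1:3, the UK ratio would be (8,342 × 2.22 + 8,545 × 3)/16,887 = 2.61.

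Empagliflozin person-time is 32,085 + 54,968 + 34,711 = 121,764, a UK share of 26%. DPP-4 person-time at the lower ratio is 71,229 + 89,598 + 59,356 = 220,183, a UK share of 32%; at 2.61 it is 36%. With a hazard ratio of 1 in every country:

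| Outcome | Empagliflozin | DPP-4 (UK 2.22) | Ratio | DPP-4 (UK 2.61) | Ratio |
|---|---|---|---|---|---|
| Urinary tract | 149.7 | 146.5 | 1.02 | 144.7 | 1.035 |
| Bladder | 89.3 | 87.3 | 1.02 | 86.2 | 1.04 |
| Renal | 53.6 | 51.5 | 1.04 | 50.1 | 1.07 |

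With the same country weights for both drugs, every ratio is 1.00.

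**The case against.** The comparative objective is the adjusted hazard ratio, and nothing here shows it to be biased. Covariates at or above 10% enter the base and adjusted models, calendar year of index is among the candidates, and the unweighted balance check would probably flag it. This stands. The protection is large but not complete, because SAP 6.7.2 requires five events per category. Sweden 2020, with all 10,494 eligible patients and 0.25 years each, would have about 4.3 expected urinary tract cancers. Unbalanced year indicators or collapsed years could still enter.

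The risk trend is assumed, and 10% per year is strong: 1.1^5 = 1.61-fold over index years 2015 to 2020. This also stands, so the crude bias is stated as conditional.

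The pooled-rate artefact is small against noise. With about 182 expected empagliflozin urinary tract events the 95% interval is roughly -14%/+16%; with about 65 renal events it is roughly -23%/+27%. The SAP plans no pooled rate ratio, and the forest plots show rates by country. That lowers the weight of the point, but the artefact is systematic, always in the same direction here, and avoidable.

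The SAP has other safeguards: the 1:1 sensitivity analysis, re-evaluation of the matching if many variables stay unbalanced (SAP 6.6.2), and a review of heterogeneity before pooling (SAP 6.7.3). The first avoids the problem only in its own output; the other two may help but commit to no repair. Relaxing the time window did not reduce the raw imbalance in the simulation (Sweden 28% at 90 days, 38% at 365 days), though the wider window was run once, without the propensity score. SAP 6.8 and 6.9 are not in the public text and could say more.

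**Conclusion.** The point holds for the crude hazard ratios, by-drug rates, Kaplan-Meier curves and pooled rates, and should be fixed. The index-year imbalance in the raw pools would pass the SAP's own limit in Sweden, Finland and GOLD on idealised eligible counts; the matched counts will differ. Bias in the crude outputs is about 1-2% at a 5% yearly risk trend and up to about 4% at 10%, in either direction, and nil without a trend. The pooled-rate excess of about 2-4% (urinary tract, bladder) and 4-7% (renal) needs no trend assumption, only the protocol's country rates and the achieved ratios.

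Three stronger readings are tempting and not supported:
- That the primary hazard ratios are biased. Country mix cannot reach them, because they are estimated within country and then combined, and the adjustment rule largely covers index year.
- That every Cox model must be weighted. For models that already adjust for imbalance, this trades power for little gain.
- That the pooled rates would show a 7-10% excess. This follows only at the planning ratios of 3, 1 and 2 (1.066, 1.085 and 1.104), not under the variable matching that the SAP specifies.

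**What to change.** - (a) Compute the pooled rates for both drugs with the same country weights, for example empagliflozin person-time in each country. This costs no hazard-ratio power.
- (b) In the crude hazard ratios, by-drug rates and Kaplan-Meier curves, weight each comparator by 1/(number of comparators in its set), with variance clustered on matched set. Report weighted standardized differences beside the unweighted ones. Keep the unweighted ones as the trigger for adjustment: they describe the pools that the unweighted base and adjusted models use, and dropping them could remove index year from those models.
- (c) Leave the base and adjusted Cox models unweighted, or add a weighted version as a sensitivity analysis. Weighting lowers the effective comparators per initiator from 1.71 to about 1.42 (Finland), 1.63 to 1.34 (Sweden) and 2.22 to 1.88 (GOLD). Approximate power at HR 1.5 for urinary tract cancer would fall from 77.4% to 73.7%, from 92.6% to 90.0%, and from 63.1% to 60.1% (UK at the GOLD ratio), or about 3-4 points.
- (d) Reconcile exact index-year matching in SAP 6.3 with the 90-day window in SAP 6.5.2.

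The cost is SAP wording, a few lines of code and slightly wider intervals for the crude outputs.
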